This study will represent the first intervention of mifepristone on yohimbine-induced alcohol craving and consumption in this population. As this is a safety and tolerability study, adverse events evaluation (AEE) will be reported as the number and their intensity. We will compare the number and intensity of AEE in the mifepristone vs. placebo groups weekly and during the alcohol laboratory sessions. These events will be rated as none, mild, moderate, and severe. Paired *t*-tests will be used to test for medication effects. Generalized Estimating Equations (GEE) will be used for dichotomous data if events are rare. To guard against Type II errors, we will also report additional descriptive data on adverse events (the distribution of the maximum level of an adverse event collapsed across time points per condition). This study integrates self-reported and clinician-administered assessments with clinical laboratory analysis. A series of analyses of covariance (ANCOVA) will be conducted to test the effect of mifepristone on alcohol craving while controlling for variance

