Center Alcohol and Addiction Studies

Brown University

TITLE: A Pilot Study on the safety and efficacy of Mifepristone for the prevention of relapses of alcohol drinking

PI: [name]

NCT02243709

IND121984

DATE: December 15 2014

Statistical analysis

Distributional characteristics of outcome measures were examined to evaluate similarity to the normal distribution, detailed descriptive analysis of demographics, substance use, and clinical characteristics were conducted. Comparisons with these characteristics, in relation to enrolled versus completer status, were performed using *t*-tests to analyze continuous variables (e.g., age) and Chi square (χ^2) for categorical variables (e.g., sex, race, smoking status). Attrition rates between the screening visit and follow-up visit were examined descriptively to assess for potential bias. In addition, a logistic regression was performed to test for possible bias due to period (A/B: placebo first, then mifepristone and B/A: mifepristone first, then placebo) or medication carryover (1: placebo and 2: mifepristone), as done in our prior cross-over trial¹.

Primary outcomes: safety and tolerability of oral administration of mifepristone was assessed after 7 days in outpatient setting, and when it was administered with yohimbine and alcohol during the laboratory paradigms. These analyses included comparing the number of adverse events (AEs) between the mifepristone and placebo condition via a χ^2 test. The results were presented using summary statistics such as number of subjects (*n*); mean (*M*); standard deviation (*SEM*) or frequency distributions (%).

Primary outcomes: safety and tolerability assessed by the number of adverse events (AEs) of oral administration of mifepristone was assessed after 7 days in an outpatient setting, and when it was administered with yohimbine and alcohol during the laboratory paradigms. Additional safety and tolerability analysis included hemodynamic response, alcohol pharmacokinetics, and subjective effects of alcohol between the mifepristone and placebo condition (χ^2 test).

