Secondary outcomes: Craving measures included alcohol craving questionnaire short form-revised (ACQ-SF-R)². Values of the water trials for each dependent variable were inserted as covariate in the model (allowed for the dependent variable to be specific for alcohol), time coded: t_1 =alcohol trial 1 and t_2 =alcohol trial 2. In the bar laboratory, alcohol consumption was measured by number of drinks consumed (*t*-test). In the outpatient setting, alcohol consumption was measured by self-report using the timeline follow back method, reported as heavy drinking days and drinks per week.

All statistical analysis was performed after participants had their follow-up visit and the study database had been locked. All the statistical procedures were performed by IBM SPSS Statistics for Windows, version 27 with Macro MEMORE extension⁹ (IBM Corp., Armonk, NY, USA) and GraphPad Prism (v.5) was used to generate figures (La Jolla, CA, USA). The effect sizes were calculated as η^2 for GLM and Cohen *d* for *t*-test. All statistical tests were two-tailed, and statistical significance was accepted if an alpha value $p<.05$ was obtained.

For all outcomes, we utilized an intention-to-treat (ITT) approach, where participants were examined based on their *a priori* randomized protocol and received at least one dose of the study medication

(mifepristone or placebo)³. All analyses were conducted using Generalized Estimating Equations (GEE)⁴ with robust standard errors, and an unstructured correlation matrix, unless noted.

Power

This was a proof-of-concept trial to demonstrate the feasibility of the combined study design, the safety and tolerability of mifepristone and yohimbine while consuming alcohol, and the potential value of testing mifepristone in an appropriately-powered larger RCT. In selecting a target sample size, we balanced power considerations and feasibility given the translational nature of this trial. Because of the within-subjects design, power to test the effects of study drug is optimized for this modest sample size (originally $N=20$ then, after additional funding, increased to $N=32$). For the safety and tolerability outcomes (primary) adverse events difference was detected based on a judgement concerning the minimal effect which has clinical relevance in the management of patients. In a noninferiority trial, the exact sample size cannot be fixed in advance because it depends upon the chosen stopping guideline⁵.

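### The protocol assigns GEE to rare dichotomous adverse events with no link and no zero-event rule, the SAP names an unpaired chi-square test instead, and neither suits sparse paired data

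*Protocol*

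**What the plan says.** The protocol's Data analysis section sets out the AE comparison: "We will compare the number and intensity of AEE in the mifepristone vs. placebo groups weekly and during the alcohol laboratory sessions". Its default test is "Paired *t*-tests will be used to test for medication effects". For binary AE data it adds "Generalized Estimating Equations (GEE) will be used for dichotomous data if events are rare". It backs this with a description of the maximum AE level per condition: "To guard against Type II errors, we will also report additional descriptive data on adverse events".

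The SAP, Statistical analysis, makes safety and tolerability the primary outcome and names a different test: "These analyses included comparing the number of adverse events (AEs) between the mifepristone and placebo condition via a χ^2 test". It sets a general default, "All analyses were conducted using Generalized Estimating Equations (GEE", qualified as "with robust standard errors, and an unstructured correlation matrix, unless noted". The chi-square test for AEs is one of the exceptions so noted. The significance rule is "All statistical tests were two-tailed, and statistical significance was accepted if an alpha value $p<.05$ was obtained".

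Neither document defines a rare event, states a link function, says what to do when a condition has no events or a model fails to converge, or names an exact, McNemar or penalised method.

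**The concern.** The design is a two-period crossover, so each participant who completes both periods contributes one outcome per condition. With a few dozen participants, an uncommon event may well occur under one condition only. A GEE with a logit link then has no finite treatment estimate. This is separation, not the usual small-sample bias of robust standard errors, so a standard-error correction does not cure it.

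Safety is the primary outcome, and uncommon events are where a false alarm or a missed signal matters most. Under the protocol's rule, a split of one event to none could be printed as highly significant, as clearly non-significant or without any p-value, depending on the software's stopping rule. The SAP's test avoids that failure but treats two observations on the same person as two people. An analyst holding both documents also cannot tell which test governs.

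**Working it through.** **Inputs.** The SAP (Power) gives N=20, later 32. The protocol synopsis expects 50 completers. Alpha is 0.05 two-sided (SAP). The documents give no planning AE rate per condition, so I assume risks of 2% to 10%, equal and independent between conditions, with complete pairs. The logit link is also assumed. The documents give no figure of their own to reproduce here.

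**Step 1: why an empty condition breaks the fit.** With *a* of *n* participants having the event on mifepristone and *b* of *n* on placebo, the fitted log odds ratio is ln[a/(n−a)] − ln[b/(n−b)]. If b=0, the second term is −∞ and the estimate is +∞. If a and b are both between 1 and n−1, it is finite.

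**Step 2: how often this happens.** Let q=(1−p)^n be the chance that one condition is empty. Exactly one empty condition has probability 2q(1−q). Both empty has probability q². For N=32:

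| Risk p | q | Exactly one empty | Both empty |
|---|---|---|---|
| 2% | 0.98^32 = 0.524 | 2×0.524×0.476 = 50% | 27% |
| 3% | 0.97^32 = 0.377 | 2×0.377×0.623 = 47% | 14% |
| 5% | 0.95^32 = 0.194 | 2×0.194×0.806 = 31% | 4% |
| 10% | 0.90^32 = 0.034 | 2×0.034×0.966 = 7% | 0.1% |

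When both conditions are empty there is no contrast and no method can test one, so those cases do not count against GEE. The same formula for exactly one empty condition gives 44%, 50%, 46% and 21% at N=20, and 46%, 34%, 14% and 1% at N=50, for the four risks in order. Within-person correlation matters little: at N=32 the chance of at least one empty condition is 77%, 35% and 7% at 2%, 5% and 10% risk under independence, and 71%, 33% and 6.5% with correlation 0.3.

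**Step 3: what the fit then reports.** These are paired logit GEE fits with robust standard errors, N=32, no participant having the event in both conditions. Newton steps were stopped at set counts, and the same tables were fitted with a standard Python routine.

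| Events | 5 steps | 10 steps | 20 steps | Python routine | Exact McNemar |
|---|---|---|---|---|---|
| 1 v 0 | p=0.007 | p=5×10⁻¹⁴ | undefined | p=0.93 | 1.00 |
| 3 v 0 | p=5×10⁻¹⁰ | p=2×10⁻⁴⁵ | undefined | no SE | 0.25 |
| 3 v 1 | p=0.34 | p=0.34 | p=0.34 | p=0.34 | not shown |

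The 3 v 1 row is the control. The log odds ratio is 1.17 with SE 1.21 at every step count, and the unstructured correlation gives the same result. The empty condition is the cause.

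**Step 4: the SAP's chi-square test.** Counting participants with the event, 5 of 32 v 0 of 32:

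- Pearson chi-square = 64×(5×32 − 27×0)² / (5×59×32×32) = 64×25,600/302,080 = 5.42, p=0.020. The smallest expected count is 2.5.
- Exact McNemar, with 5 discordant pairs all one way: 2×0.5⁵ = 0.0625.

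The conclusion at 0.05 changes with the method.

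**Step 5: what exact McNemar can and cannot do.** It gives a p-value in each of these one-empty-condition tables. With all discordant pairs one way, 5 pairs give 0.0625 and 6 give 2×0.5⁶ = 0.031, so at least 6 discordant pairs are needed for p<0.05. Discordant pairs follow a binomial distribution with n=32 and probability 2p(1−p). Enumerating the rejection region gives a type I error of 0.00004 at 2% risk, 0.002 at 5% and 0.012 at 10%, far below the nominal 0.05.

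**The case against.** The strongest reply is that GEE is not the trial's primary AE test. The SAP names chi-square for the number of AEs, its GEE default yields where another test is noted, and the protocol's own default is a paired t-test. This stands. A reader might infer that the primary safety comparison as a whole gives arbitrary or missing p-values, and the documents do not support that. The failure belongs to the protocol's rule for rare dichotomous AEs. The chi-square test does not rescue the plan, though, because it ignores pairing and the two documents name different tests.

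Second, the link is not stated. With an identity link, GEE at N=32 gives finite results (3 v 0, p=0.069; 1 v 0, p=0.31). This stands too, although finite does not mean well calibrated. The infinite estimate follows from the conventional link and is not forced by the written rule.

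Third, a reader might infer that rarity itself breaks the method, so that the rule is simply backwards. The trigger is an empty condition: 3 v 1 fits stably, and at 10% risk about 93% of comparisons have events in both conditions. Striking cases such as 10 v 0 (Python routine p=0.97, exact 0.002) or 6 v 0 (no SE, exact 0.031) show the mechanism, but 31% and 19% on mifepristone are not plainly rare.

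Fourth, exact McNemar has limits: low power with rare events, complete pairs only, and no built-in handling of the weekly and session comparisons. All of this stands and shapes the fix.

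Finally, this is a pilot with a descriptive AE summary already planned. That lowers the severity but does not settle which test applies.

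**Conclusion.** The concern holds in a limited form. The protocol sends rare binary AEs to a method with no stated link and no rule for an empty condition. Under a logit link, that situation arises in about 50%, 47%, 31% and 7% of comparisons at 2%, 3%, 5% and 10% risk with N=32, and the resulting p-value cannot be interpreted. Splitting AEs by week and session makes empty conditions more likely. The SAP's alternative yields a p-value, but from an unpaired test on paired data, and the two documents disagree.

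This rests on assumed AE risks that are equal and independent between conditions, complete pairs and an assumed logit link. The chi-square figures further assume that participants, not individual events, are counted. SPSS, the SAP's software, was not available, so its output with an empty condition is unknown. Severity is moderate. The evidence does not support calling it a must-fix defect of the primary analysis.

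**What to change.** In both documents, replace the conflicting provisions for dichotomous AEs with one method:

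- For each participant and condition, record whether at least one event occurred, and state the time window that this covers.
- Compare conditions by the exact McNemar test. Report the paired risk difference with a score or exact 95% confidence interval.
- Describe participants with only one period separately, since the SAP's intention-to-treat set requires only one dose and such participants cannot enter a paired test.
- Delete the protocol sentence assigning GEE to rare events. Any GEE on AEs is supportive, has its link stated, and is reported only when both conditions have events.

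The cost is a sentence or two in each document. The statistical price is real: exact McNemar is clearly conservative for rare events and uses complete pairs only. A non-significant result must therefore not be read as evidence of safety, and the risk difference with its interval should carry the interpretation.

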Translating preclinical paradigms into effective models for assessing pharmacological approaches for stress-induced alcohol relapse in humans requires a comprehensive model capable of integrating: alcohol-proximal variables that influence drinking (withdrawal symptoms, craving), neuroendocrine variations (cortisol), and stress-risk factors (different temporal traumatic events). A comprehensive stress model is needed because emotional distress, neuroendocrine activation, stress-related genetic variations, craving, and alcohol consumption do not necessarily overlap in alcohol-dependent individuals. Mifepristone may be a valuable pharmacotherapeutic strategy for preventing relapse to AUD, and yohimbine is a pharmacological stressor capable of increasing craving, creating recall of traumatic memories, and altering neuroendocrine levels in alcohol-dependent individuals. As FDA-approved medications, both mifepristone and yohimbine have the advantage of being directly applicable to an alcohol clinical setting and being utilized in the translational efforts described in this application.

The overall objective of this study is to conduct a randomized pilot laboratory study consisting of a placebo-controlled assessment of the effects of 600 mg of mifepristone for a week, in a stress-induced condition triggered by a single dose of 32.4 mg of yohimbine in non-treatment-seeking-alcohol-dependent individuals. In the following specific aims, I propose:

Aim 1: to assess the safety and tolerability of mifepristone and yohimbine while consuming alcohol. Randomized participants will complete two alcohol laboratory sessions along with a battery of physiological and psychological assessments that measure adverse events and pharmacokinetic (PK)/pharmacodynamic (PD) interactions.

Aim 2: to test the hypothesis that an increase in alcohol craving induced by yohimbine is antagonized by pre-administration with mifepristone. To test this hypothesis, we will establish the effect of mifepristone on alcohol cue-elicited craving during a cue-reactivity (CR) experiment along with a series of physiological and psychological tests assessing alcohol craving.

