Medications and doses: Participants receive an oral dose of 600 mg of mifepristone or matching placebo for approximately seven days (plus three extra pills). Participants will receive detailed information on the study medications, including their current use and possible side effects. Mifepristone treatment in clinical setting has shown to be safe, tolerable, and acceptable⁸⁷⁻⁸⁹, including in participants suffering from depression, anxiety, and PTSD⁹⁰⁻⁹². On Days 7 and 44, all participants will receive a single oral dose of 32.4 mg yohimbine approximately one hour ($t_{max}=1$ hour) prior to the lab session. The oral dose of yohimbine for this study is based on prior studies in which yohimbine was administered to examine neuroendocrine probe in human studies^{57,93,94}. Ample data support the safe use of yohimbine to induce craving in alcohol-dependent individuals⁵⁷, and the safe induction of stress in PTSD veterans⁹⁵ and gamblers⁶⁰. We already obtained the Investigational New Drug (IND#121984) from FDA that determined that the clinical investigation of mifepristone and yohimbine while consuming alcohol is safe to proceed (see attaché letter form FDA). Our IND was also cross-referenced by the IND of Corcept Therapeutics (IND#059737) for chemistry, manufactory, pharmacological, and toxicology data of mifepristone (see attached letter form Corcept). Participants will receive detailed information on the study medications, including their current use and possible side effects.

STUDY PROCEDURES:

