Visits 3 and 5 (Stress-induction and Alcohol Laboratory Session): All procedures and responsibilities of each member of the research team are described in Appendix Z (page 3 and 5). Participants will be instructed not to consume alcohol for 24 hours and must have a BrAC of 0.00 prior to any assessment. A sample of salivary cortisol will be collected and a single oral dose of 32.4 mg yohimbine will be administered to participants. The lab-session will begin one hour later in order to allow yohimbine to take effect⁹⁶, at which time a second sample of cortisol will be collected. The CR will be run first, followed by the ASA (Assessments Schedule, Appendix Z). The PI will schedule Visit #3 and Visit #5 (alcohol laboratory sessions) only if [name] will be in proximity of CAAS laboratory. The PI will not schedule Visit #3 and Visit #5 if both study physicians are traveling or not in Providence.

Cue-reactivity (CR). The CR will be similar to previously published studies^{73,97-101}. The entire procedure takes about 45 minutes. The water trial provides a controlled baseline that controls for all aspects of stimuli and movement, except for the nature of the beverage. Next, participants will undergo two 3-minute alcohol cue exposure trials that will be identical to the water trial except that the glass of water will be replaced with their preferred alcoholic beverage and the bottle of water will be replaced with the appropriate commercially-labeled alcohol bottle. After every 3-minute beverage exposure, participants will rate their urge to drink alcohol by completing the alcohol urge and craving questionnaire (ACQ) to assess attention to the sight and smell of water and alcohol cues. Saliva (weight in cotton rolls, mg), heart rate (HR; beats/min) and blood pressure (systolic, diastolic, and mean arterial pressure-MAP) will be monitored continuously using a Dinamap Adult Vital Signs Monitor. After the conclusion of the CR, participants will undergo the ASA. Consistent with recommendations¹⁰², participants will be informed they will receive alcohol following the CR. The last of salivary cortisol (by spitting in a tube) will be collected at the end of the CR.

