attributed to stress and anxiety level. The dependent variables will be baseline and post-laboratory session scores of Alcohol Urge and Craving Questionnaires (ACQ), Alcohol Visual Attention Scale (A-VAS) and Alcohol Attention Scale (AAS). The covariates will be trauma experienced as measured by Life Event Checklists (LEC), stress level measured by Perceived Stress Scale (PSS) and PTSD (PCL) Checklist scores, and anxiety level measured by Hamilton Anxiety Rating Scale (HAM-A), Self-Evaluation Questionnaire for state (STAI-y1) and Self-Evaluation Questionnaire for trait (STAI-y2). To examine the relationship between mifepristone compared to placebo on neuroendocrine fluctuations, we will use repeated measures ANCOVA with the cortisol baseline curve (three time-points: neutral, yohimbine challenge and after cue-reactivity) change during the laboratory sessions. Finally, to examine the effect of mifepristone compared to placebo in increasing the alcohol consumption during the alcohol self-administration, we will utilize an analysis of variance (ANOVA) with repeated measures. We will also attempt to establish an effect size for applying this paradigm on craving and drinking. These dependent measures will be operationalized by the ACQ and the ml of alcohol consumed during the drinking session, respectively. An effect size also will be obtained so that a target sample size to ensure adequate statistical power may be calculated for future proposed studies. Naturalistic drinking will be tracked via Alcohol Timeline Followback (TLFB) outside of the lab at each visit (by keeping track of the drinking behavior in the participants' calendar).

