#19 and 20 Restlessness and Nervousness (so anxiety is inferred), score >3

- Drinking Inventory consequences, (DrInC) (please see Appendix L)

Specific questions and scores that will trigger a call to the study physician:

#34 I have lost interest in activities because of my drinking (so depression is inferred), score >3

- Hamilton Anxiety and Depression Rating Scale (HAM-A; HAM-D) (please see Appendices O and O2)

in addition to being utilized as research outcomes, in our proposed study, these measures are used to monitor participants' anxiety and depression during the course of the trial. These assessments are critical to assess anxiety (HAM-A) — especially during yohimbine administration — and monitor for possible symptoms of depression that can lead to suicidality (HAM-D). It is important to know the clinical state of each participant before initiating any procedure.

Overall: To monitor for anxiety we will use the Hamilton Anxiety rating scale (HAM-A) and for depression we will use the Hamilton Depression Rating scale (HAM-D). Each item of the HAM-D is rated from 0 (not present) to 4 (severe) with a total score range from 0 to 56, where <17 (mild severity), 18-24 (mild to moderate) and 25-30 (moderate to severe). We will alert the study physician with a score of >24.

Specific question in the HAM-D and score that will trigger a call to the study physician:

#3 Suicide: *Feel life is not worth living* (so suicide may be considered), score >0

- Self-Evaluation Questionnaire (STAI y1/2) (please see Appendix R and S)

Overall: State-Trait Anxiety Inventory (STAI) -y1 and -y2, which are a commonly used measure of trait and state anxiety. The STAI has 40 items allocated to each of the State-anxiety and Trait-anxiety subscales. Responses for the S-Anxiety scale assess intensity of current feelings "at this moment," and the T-Anxiety scale assesses frequency of feelings "in general" from 1 (never) to 4 (always). We will alert the study physician to a score of > 60 on each subscale.

Specific question:

#22 *I feel nervous and restless* (so anxiety is inferred), score >3

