Yohimbine: The oral dose of yohimbine for this study is based on prior studies in which yohimbine was administered to examine neuroendocrine probe in human studies. Ample data support the safe use of yohimbine to induce craving in alcohol-dependent individuals, and the safe induction of stress in PTSD veterans and gamblers. In this study, yohimbine (32.4mg) is administered below the therapeutic index to a dose considered dangerous (>100mg). Furthermore, yohimbine will be administered only once, during the laboratory session and under direct supervision of the study personnel. It will be given at a safety-tested dose to increase noradrenergic activity already being evaluated in psychiatric individuals with clinically relevant stress conditions such as PTSD, anxiety, and depression. Finally, yohimbine's short half-life ($t_{1/2} = 1-2$ hour) provides a transient effect. The protocol includes close monitoring of blood pressure, heart rate, and cortisol levels by [name] or research laboratory staff, and we have [name] on call. In addition, the Hamilton Anxiety Rating Scale (HAM-A) (Appendix O), Self-Evaluation Questionnaire for state (STAI-y1) and Self-Evaluation Questionnaire for trait (STAI-y2) (Appendix R and S) to assess and compare anxiety at baseline and prior to releasing the participants after laboratory session are included in the assessments (**Appendix Z**). If anxiety is higher at the end of the study we will call [name] to have him meet with the participant before release. The most common side effects reported by the use of yohimbine are: an allergic reaction, irregular or fast heartbeat, confusion, dizziness, anxiety, irritability, or nervousness, tremor, headache, skin flushing.

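### The protocol's craving analysis uses a post-session score taken after self-chosen drinking, not the cue-reactivity ratings that match Aim 2 and that the SAP analyses

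*Protocol*

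**What the plan says.** Aim 2 (protocol, Study Aims) states the hypothesis that mifepristone antagonises the craving that yohimbine induces. It says how this will be tested: "we will establish the effect of mifepristone on alcohol cue-elicited craving during a cue-reactivity (CR) experiment", along with other tests of craving.

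The CR section collects the rating that this needs: "After every 3-minute beverage exposure, participants will rate their urge to drink alcohol by completing the alcohol urge and craving questionnaire (ACQ". There is a water trial and then two alcohol trials, all before any alcohol is given.

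The protocol's Data analysis section specifies something else for the craving ANCOVA: "The dependent variables will be baseline and post-laboratory session scores of Alcohol Urge and Craving Questionnaires (ACQ", and the same sentence adds the A-VAS and AAS. The section later says that the craving effect size for planning will be operationalised by the ACQ, and gives no time point.

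The SAP (Secondary outcomes) uses the short form of the ACQ from the cue trials, "time coded: t_1 =alcohol trial 1 and t_2 =alcohol trial 2", with the water-trial value as covariate. The two documents carry the same date, and neither mentions the difference.

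**The concern.** The session does not end with CR. It goes on through the priming drink and the free-choice drinking of the self-administration (ASA) experiment. A score taken after the session therefore comes late relative to the stressor, and after an amount of alcohol that the participant chose. That amount is the Aim 3 outcome.

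Two things are at stake. First, if the protocol text is followed, the Aim 2 test estimates late craving after drinking. An effect at the cue exposure could be diluted, and a treatment difference in drinking could move the craving score either way. Second, Objective B asks for an effect size to plan a larger trial. The ACQ is given after each cue exposure, around the prime, every 30 minutes of free choice and after the session. Without a time point, the planning figure is undefined.

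**Working it through.** The plan gives no calculation that depends on when craving is measured, so there is no figure to reproduce. The check adds up the stated times, derives the yohimbine level at each, and asks what else differs between the two scores.

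**Inputs, all from the protocol.** Yohimbine is given about 60 minutes before the session, with a stated tmax of 1 hour (Medications and doses). Its half-life is 1 to 2 hours (Yohimbine). CR takes about 45 minutes and is followed by ASA (Visits 3 and 5; Cue-reactivity). The prime targets 0.03 g/dl, and a 40-minute wait follows. Free choice lasts 120 minutes at 0.015 g/dl per drink, and drinking stops at BrAC 0.1 (Alcohol Self-Administration). The session lasts about 6 hours.

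**Step 1, timeline.** From dose to end of CR: 60 + 45 = 105 minutes. To the end of the wait: 105 + 40 = 145. To the end of free choice: 145 + 120 = 265, which is 205 minutes past tmax.

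**Step 2, yohimbine level.** Share of peak = 0.5^((t − 60)/h), with t in minutes after the dose and h = 60 or 120.

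| Time after dose | h = 60 | h = 120 |
|---|---|---|
| 60 min, CR starts | 100% | 100% |
| 105 min, CR ends | 0.5^0.750 = 59.5% | 0.5^0.375 = 77.1% |
| 145 min, free choice starts | 0.5^1.417 = 37.5% | 0.5^0.708 = 61.2% |
| 265 min, free choice ends | 0.5^3.417 = 9.4% | 0.5^1.708 = 30.6% |
| 360 min, if 6 h ran from the dose | 0.5^5 = 3.1% | 0.5^2.5 = 17.7% |

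As a sensitivity check, I assumed a one-compartment oral curve that peaks at 1 hour. It gives 84% to 88% at the end of CR and 18% to 36% at 265 minutes. Under both models most of the peak level has gone by the end of free choice.

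**Step 3, alcohol before the score.** At CR there is none: BrAC must be 0.00 at the start, and the prime comes later. After ASA, nominal exposure runs from 0.03 g/dl (prime only) up to the 0.1 stop. That is a spread of 0.07 g/dl, or 0.07/0.015 = 4.7 drinks before any elimination. To a first approximation,

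post-session contrast = δ + γ × Δ,

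where δ is mifepristone's direct effect on late craving, Δ its effect on the number of drinks (Aim 3), and γ the change in ACQ per drink. The documents give neither γ nor Δ, and γ could have either sign. At the cue trials the γ × Δ term is absent.

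**Step 4, the texts side by side.**

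| Source | Craving score | Before alcohol? |
|---|---|---|
| Study Aims, Aim 2 | cue-elicited, in CR | yes |
| Protocol, Cue-reactivity | ACQ after each exposure | yes |
| Protocol, Data analysis | baseline and post-session | no, for the post-session score |
| SAP, Secondary outcomes | ACQ short form, alcohol trials 1 and 2, water-adjusted | yes |

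The protocol's Data analysis section is the odd one out. The same section gives cortisol its own time point after cue-reactivity, which suggests that post-session means something later.

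**The case against.** The strongest reply is that the trial already does the right thing. CR ratings are collected near peak yohimbine and before alcohol, and the SAP analyses them. This stands, and it limits the point. A reader might infer that the trial cannot measure cue-induced craving; the documents do not support that. The comparison of mifepristone with placebo also remains randomised and within person at the later time; it simply estimates a different quantity.

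Aim 2 also mentions further craving tests, so a pre/post-session score is not outside the aim. True, but it is a weaker measure of it, and the protocol makes it the tested one.

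The post-session score has no clock time in the supplied text, and Appendix Z, which holds the schedule, is not supplied. Reading it as after drinking is an inference, though a strong one.

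Four further inferences go too far:

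- **The stressor has worn off.** Some 9% to 36% of peak remains across the two models, and a drug level is not the same as an effect.
- **The score is delayed by many more hours until BrAC reaches 0.00.** Such times need an elimination rate that the documents do not give. The longest of them also ignore the stop at 0.1.
- **The anxiety comparison has the same fault.** The Yohimbine section sets it just before release as a safety check, and that timing suits its purpose. Alternative Design Considerations and the Alcohol withdrawal text both report no rise in anxiety with yohimbine. The Data analysis section uses anxiety scores as covariates, not outcomes.
- **The outcome was switched after results were seen.** The SAP carries the protocol's 2014 date, yet it is written in the past tense and cites a November 2021 paper. That leaves the timing of its craving definition unclear, but does not show that the choice was driven by data.

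**Conclusion.** The point holds as a fault in the protocol's analysis text and an unexplained difference from the SAP. As written, the Data analysis section tests Aim 2 with a score taken at least 265 minutes after yohimbine. About 9% to 31% of peak then remains (18% to 36% under the alternative model), against roughly 60% to 100% during CR. The score also follows self-chosen drinking that treatment may affect.

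This assumes that post-session means after ASA, that the stated durations apply, and that free choice runs its full 120 minutes. A participant stopped early at BrAC 0.1 would finish drinking sooner, but at the highest permitted alcohol level, so the mixing with intake remains. The size of any bias cannot be computed from the documents.

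The change is worth making because the planning effect size for the larger trial depends on it. It does not threaten the trial, since the right ratings exist.

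**What to change.** In the protocol's Data analysis section:

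- Replace the baseline and post-session craving scores with the ACQ ratings after the two CR alcohol trials, with the water-trial rating as covariate, as in the SAP. Use one name for the instrument in both documents.
- Name these ratings as the Aim 2 outcome and as the source of the Objective B craving effect size.
- Label ACQ ratings during free choice and after the session as descriptive.
- If the A-VAS and AAS stay as craving outcomes, say when each is taken, or point to Appendix Z.
- Record the change with its date and reason, so that a reader can see when the craving outcome was settled.

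Leave the pre-release anxiety check as it is. The cost is wording and a dated note. The ACQ ratings are already collected, so no visit, form or participant burden is added.
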